4.6. Measures to Minimize Bias

4.6.1. Randomization

At screening, subjects will be assigned a subject identification number. When a subject is confirmed to be eligible for the clinical study, he/she will be randomized.

A total of approximately 750 subjects will be randomized in a 1:1:1 ratio to receive GLPG1690 600 mg q.d., GLPG1690 200 mg q.d., or matching placebo for at least 52 weeks. Allocation of each subject to a given treatment will be described in a randomization list prepared by a CRO. This randomization list will be stratified in a balanced manner for background local standard of care for treatment of IPF (nintedanib, pirfenidone, or neither). Recruitment may stop earlier in one or more strata to maintain the balance as indicated, while the other strata(s) continue to recruit. Upon qualification for the study, allocation of each subject to a given treatment will be done using a centralized electronic system (interactive web response system [IWRS]) with permuted blocks.

For each subject at each visit, the clinical study center will contact the IWRS for the appropriate treatment number to be assigned. Each medication kit will contain the relevant IMP for the period until the next visit.

Subjects and study personnel will be blinded to the treatment assignment. Additional details on blinding and unblinding are provided in Section 4.6.2.

4.6.2. Blinding and Unblinding

This is a randomized, double-blind clinical study. The subject and the entire clinical study team, including the investigators, clinical study coordinators, and sponsor personnel are blinded to treatment assignment, except for situations described in the last paragraph of this section.

Blinded and packaged medication will be provided to the clinical study center. All IMP formulations will be packaged in the proper proportion to assure desired dosages and maintenance of the blinding. In case of down-titration, interruption, or re-escalation, a sham dose level is available for the treatment allocation arm of GLPG1690 200 mg in order to ensure the same number of steps as the other treatment allocation arms and to ensure blinding (for details, refer to Sections 4.1 and 5.2). The different steps are blinded for treatment allocation but not for dose level.

The blind can be broken only if the investigator deems it necessary for the safety of a subject. The investigator is encouraged to discuss considerations to break the blind with the CRO medical monitor (as per study contact list) or the sponsor's study physician (in case the former is not available), whenever possible and where the situation allows. However, the responsibility to break the treatment code in emergency situations resides solely with the investigator. The investigator is not required to discuss unblinding beforehand if he/she feels rapid emergency unblinding is necessary, but is required to inform the CRO medical monitor and sponsor in a timely fashion after unblinding has occurred.

The blind can be broken by the investigator via the IWRS. If the blind is broken for any reason during the course of the study, the moment on which the subject's data were unblinded and all other relevant information will be documented by the clinical study center, the CRO, and other sponsor designees, as appropriate. The reason for breaking the blind will be indicated and justified in the source documentation and in the CRF.

Code-break information (via IWRS vendor/randomization list) will be provided to the bioanalytical laboratory responsible for plasma drug determination sample analysis and to the sponsor pharmacovigilance lead for SAE reporting purposes. The IDMC will have access to unblinded data (for details, refer to Section 8.1).

5. INVESTIGATIONAL MEDICINAL PRODUCT

5.1. Identity of the Investigational Medicinal Product

The IMPs (GLPG1690 and placebo) will be supplied to the clinical study center, by and under the responsibility of the sponsor, who will also provide the investigator with European Union Qualified Person release documents.

GLPG1690 will be provided as film-coated tablets for oral use, containing 100 mg or 200 mg G451990 each (G451990 is the compound code for GLPG1690). The placebo will be provided as matching film-coated tablets for oral use. The GLPG1690 100-mg tablets and the placebo tablets matching the GLPG1690 100-mg tablets will be smaller than the GLPG1690 200-mg tablets and the placebo tablets matching the GLPG1690 200-mg tablets.

A full list of excipients used in the film-coated tablet formulation is available in the IB (Edition 6, 28-June-2019) and any relevant updates/addenda/errata.

5.2. Dosage and Administration

The following doses will be tested; three tablets will be provided per dose (high [original] dose level):

- GLPG1690 600 mg q.d. (as three GLPG1690 200-mg tablets)
- GLPG1690 200 mg q.d. (as one GLPG1690 200-mg tablet and two placebo tablets, matching the GLPG1690 200-mg tablet)
- placebo q.d. (as three placebo tablets, matching the GLPG1690 200-mg tablet)

The following doses will be provided for down-titration and re-escalation; two tablets will be provided per dose:

Low (reduced) dose level:

- GLPG1690 200 mg q.d. (as one GLPG1690 200-mg tablet and one placebo tablet, matching the GLPG1690 100-mg tablet)
- GLPG1690 100 mg q.d. (as one GLPG1690 100-mg tablet and one placebo tablet, matching the GLPG1690 200-mg tablet)
- placebo q.d. (as one placebo tablet, matching the GLPG1690 200-mg tablet and one placebo tablet, matching the GLPG1690 100-mg tablet)

Intermediate (reduced) dose level:

- GLPG1690 400 mg q.d. (as two GLPG1690 200-mg tablets)

- GLPG1690 200 mg q.d. (as one GLPG1690 200-mg tablet and one placebo tablet, matching the GLPG1690 200-mg tablet)
- placebo q.d. (as two placebo tablets, matching the GLPG1690 200-mg tablet)

Refer to [Figure 2](#) in Section 4.1.2 for an overview of number of tablets to be taken per dose level.

The IMP is to be taken q.d. at the same time every day with food (e.g. breakfast, small meal, or a snack) or after food intake, taking into account the timing of the planned visits, with a maximum of 2 hours between the food intake and IMP intake. Subjects will be instructed to swallow the tablets as a whole with a glass of water and to not chew the drug prior to swallowing. On visit days, subjects will be instructed to take their IMP at the clinical study center, to allow for predose (i.e. before IMP intake) assessments to be completed.

At Visits 3, 9, and 12, the subject will be asked to take pirfenidone or nintedanib (if applicable) at the clinical study center.

If a subject misses a dose (e.g. because he/she forgot to take the medication), he/she should take the missed dose within 12 hours after the planned intake time and within 2 hours of food intake. If the IMP is not taken within 12 hours after the planned time, the missed dose should be skipped.

For subjects who are taking nintedanib as standard of care medication at screening or randomization or who start nintedanib during the study, it is recommended to take the IMP at or after lunch (approximately 4 hours after nintedanib morning intake).

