2.2. Background - Clinical Studies

2.2.1. Clinical Safety

As of the safety data cut-off date of IB Edition 6, in clinical pharmacology studies, GLPG1690 had been administered to 85 healthy subjects as single doses (dose range: 20 to 1500 mg), to 96 healthy subjects in repeated doses (dose range: 100 to 1000 mg for either 7 or 14 days).

Administration of GLPG1690 was considered safe and well tolerated during these studies. No deaths, serious treatment-emergent adverse events (TEAEs), or TEAEs leading to investigational medicinal product (IMP) discontinuation were reported after dosing with GLPG1690. All GLPG1690 TEAEs were at most moderate in severity. In Study, GLPG1690-CL-109, one SAE (ECG repolarization abnormality) was reported after a single dose of nintedanib, but before dosing with GLPG1690 (IMP).

The safety profile of single doses of nintedanib and pirfenidone in Study GLPG1690-CL-109 both alone and in combination with GLPG1690 was consistent with the respective nintedanib and pirfenidone prescribing information.

An additional DDI study (GLPG1690-CL-113) evaluated the effect of multiple oral doses of GLPG1690 on the safety and tolerability of nintedanib 150 mg twice daily (b.i.d.) under different dosing conditions; i.e. the GLPG1690 dose and the timing of GLPG1690 administration versus the nintedanib morning intake. Subjects received 150 mg nintedanib b.i.d. on Days 1 and 7, and GLPG1690 200 mg q.d. 0 (i.e. concomitantly) or 2 hours after nintedanib morning intake time, or 600 mg q.d. 0, 2, or 4 hours after the nintedanib morning intake time on Days 3 to 9. Cohorts 1 and 2 evaluated the morning and evening PK of nintedanib (150 mg b.i.d.) when administered alone and when the morning dose was administered simultaneously with GLPG1690 200 mg (in Cohort 1) or 600 mg (in Cohort 2). Cohorts 3 and 4 evaluated the morning and evening PK of nintedanib 150 mg b.i.d. when administered alone and in combination with GLPG1690 200 mg or 600 mg administered 2 h or 4 h after the nintedanib morning dose (i.e., 600 mg 2 h [Cohort 3a]; 600 mg 4 h [Cohort 3b] or 200 mg 2 h [Cohort 4a]).

There were no serious adverse events and all TEAEs were at most moderate in severity. There was one TEAE (herpes zoster) that led to discontinuation of treatment in the cohort that received GLPG1690 200 mg at the same time as the nintedanib morning dose. GLPG1690 at doses of 200 mg and 600 mg q.d. was well-tolerated.

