Nintedanib demonstrated in in vitro studies little or no inhibition of CYP enzymes 1A2, 2A6, 2B6, 2C8, 2C9, 2C19, 2D6, 2E1, 3A4, 4A11, and of uridine 5'-diphosphoglucuronosyltransferase (UGT)1A1 or UGT2B7 activities and is a weak inhibitor of P-gp. GLPG1690 is P-gp substrate and has CYP3A4 involved in its metabolism although it is expected to undergo a low first-pass effect after oral administration.

Clinical DDI studies showed that exposure of nintedanib (150 mg single dose or b.i.d. dose), as measured by C_{max} , and AUCs was approximately 2-fold greater when administered on the same day (b.i.d) as, and simultaneously with, GLPG1690 600 mg than when administered alone. The increased exposure of nintedanib was in the same order of magnitude to that observed with concomitant administration of ketoconazole (a P-gp and CYP3A4 inhibitor) and that did not warrant a contraindication in the nintedanib label, but a warning for monitoring tolerability.

The interaction (increased exposure of nintedanib) observed when GLPG1690 and nintedanib 150 mg b.i.d. were administered concomitantly was reduced when GLPG1690 was administered 2 or 4 hours after the nintedanib morning dose.

This clinical study protocol contains specific precautions and exclusions to manage use of GLPG1690 on top of standard of care (pirfenidone and nintedanib). The plasma concentrations of GLPG1690, pirfenidone and nintedanib will be collected. The potential for increased exposure to nintedanib when co-administered with GLPG1690 can be managed by separating the intake times of the morning dose of nintedanib and the IMP daily dose. It is therefore recommended that all subjects on nintedanib take IMP at or after lunch (approximately 4 hours after nintedanib morning intake); refer to Section 5.2. Additionally all subjects taking nintedanib will be evaluated by monitoring adverse events and managing them according to the guidance in the nintedanib prescribing information.

Management of adverse events

For the management of AEs, guidance for the investigator should be followed, as described in Section 4.1.2. As noted above, the investigator needs to evaluate the potential of increased exposure to nintedanib when coadministered with IMP by monitoring adverse events and managing them according to the guidance in the nintedanib prescribing information and the guidance provided in this protocol.

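### The missed-dose rule in Section 5.2 has no provision for subjects on twice-daily nintedanib, so its 12-hour late window covers the evening nintedanib dose (a minor gap that is cheap to close)

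*Protocol*

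**What the plan says.** Protocol Section 5.2 sets once-daily IMP at a fixed time with or soon after food. A subject who forgets a dose is told that "he/she should take the missed dose within 12 hours after the planned intake time and within 2 hours of food intake"; beyond 12 hours the dose is skipped. This is written for all subjects. The closing paragraph of the same section then deals with nintedanib: "it is recommended to take the IMP at or after lunch (approximately 4 hours after nintedanib morning intake"). It mentions neither late doses nor the evening nintedanib dose.

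The reason is in Section 4.4. Nintedanib exposure was "approximately 2-fold greater when administered on the same day (b.i.d) as, and simultaneously with, GLPG1690 600 mg than when administered alone". The interaction "was reduced when GLPG1690 was administered 2 or 4 hours after the nintedanib morning dose", and the protocol manages it by separating IMP from the morning dose. Section 4.4 also puts the increase in proportion: it is likened to that seen with ketoconazole, which "did not warrant a contraindication in the nintedanib label, but a warning for monitoring tolerability".

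The diary tick box in Section 6.4 asks only about the roughly 4-hour gap from the morning dose. No exception to the late-dose rule for nintedanib users appears in Sections 4.4, 4.5.3.2, 5.2, 5.5, 6.1, 6.4 or 6.7.

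**The concern.** Nintedanib is taken twice a day, and the timing advice covers only one of those two doses. Moving planned IMP to around lunch also moves the 12-hour late window, which then extends over the evening. A forgotten lunchtime dose may well be caught up at the evening meal, which meets the food condition. The rule says the subject should take it, so someone following the text could take IMP and evening nintedanib at the same moment.

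What is at stake is tolerability in the nintedanib stratum on occasional days. No endpoint, estimand, error rate or stopping rule is affected. Treatment lasts from 52 to about 132 weeks (Section 4.1), so some missed doses are foreseeable, but the documents do not say how many.

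**Working it through.** The protocol gives no figure to reproduce, so this is a check of clock times.

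**Inputs**
- Planned IMP time: P = 4 h after morning nintedanib (Section 5.2).
- Late window: 12 h after P (Section 5.2).
- Nintedanib twice daily (Section 2.2.2).
- Interval I between the morning and evening nintedanib doses: not given for trial subjects, so assumed and varied.

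**Late window.** From P to P + 12, that is 4 to 4 + 12 = 16 h after the morning dose.

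**Delay at which late IMP meets evening nintedanib.** I − 4. This is permitted if I − 4 ≤ 12, that is if I ≤ 16 h.

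| Assumed I (h) | I − 4 (h) | Within 12 h? |
|---|---|---|
| 8 | 4 | yes |
| 10 | 6 | yes |
| 12 | 8 | yes |
| 14 | 10 | yes |
| 16 | 12 | yes (limit) |
| 18 | 14 | no |

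Example with I = 12: nintedanib 08:00, IMP planned 12:00, evening nintedanib 20:00, late IMP allowed until 24:00. The next morning's nintedanib falls 24 − 4 = 20 h after planned IMP, outside the window, so only the evening dose is involved.

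**Was evening co-intake tested?** Section 2.2.1 describes study CL-113, in which GLPG1690 was given 0, 2 or 4 h after the morning nintedanib dose (600 mg at all three times, 200 mg at 0 and 2 h). With I = 12, those times are 12, 10 and 8 h before the evening dose. With I = 8 they are 8, 6 and 4 h before it, and with I = 14 they are 14, 12 and 10 h. None is simultaneous with the evening dose. Evening nintedanib PK was measured ("Cohorts 3 and 4 evaluated the morning and evening PK of nintedanib 150 mg b.i.d"), but the exposure values in Section 2.2.2 are redacted and no evening result is visible.

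**Can a minimum gap be read off the documents?** No. The reported reduction is for IMP taken after nintedanib. For IMP taken before it, Section 2.2.2 gives a half-life of about 11 h. Counting elimination alone (a simplification from a single-dose half-life), the fraction left is 0.5^(4/11) = 78% after 4 h and 0.5^(8/11) = 60% after 8 h. IMP taken a few hours before the evening dose is still largely present, and the planned lunchtime dose does not leave the evening GLPG1690-free either.

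**The case against.** A reader might infer that the late-dose rule contradicts the timing recommendation, or that it instructs subjects into a known doubling of nintedanib exposure. The documents support neither reading. The separation is a recommendation, and it concerns the morning dose; a late IMP dose moves further from that dose. The roughly 2-fold figure was observed with 600 mg taken together with the morning dose. Section 2.2.2 says the effect depends on GLPG1690 dose, and under 1:1:1 randomization about one third of the nintedanib stratum is on 600 mg, one third on 200 mg and one third on placebo.

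The opposing case goes further. The sponsor chose morning-only separation while holding evening PK data that are not shown, so the omission may be deliberate. GLPG1690 is already present in the evening on the planned schedule, so only an unestimated increment is at issue. CL-113 included simultaneous morning intake and reported that "GLPG1690 at doses of 200 mg and 600 mg q.d. was well-tolerated", with no rise in diarrhea, unlike the earlier interaction study. Section 4.4 adds a safeguard: "Additionally all subjects taking nintedanib will be evaluated by monitoring adverse events". Section 9.1.6 requires suspected drug interactions to be reported within 24 hours, and Section 4.1.2 allows dose reduction or interruption.

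Most of this stands, and it is why the point is minor. It does not remove the gap. On the timings described, the CL-113 evening data do not include IMP taken with the evening dose. The summary of Amendment 3 describes moving the intake time and mentions no adjustment to the late-dose rule. The controls detect or manage a coincidence and do not prevent it. The diary records the date and tablet count, and a negative tick shows only that the 4-hour timing was not kept, not that the two drugs were taken together.

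**Conclusion.** The gap is real and minor. As written, the rule lets a compliant subject on nintedanib take a late IMP dose together with the evening nintedanib dose, whenever the two nintedanib doses are no more than 16 h apart. That interval is assumed; the conclusion does not change anywhere in the 8 to 16 h range.

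The exposure would be isolated. The evening effect is inferred from morning data, and the 2-fold figure belongs to the 600 mg arm. How often doses are missed is not stated, so no event rate or risk is claimed. Expected harm is small, given the protocol's comparison with a label warning and the tolerability seen in CL-113. The point should be acted on because the correction is cheap and follows the sponsor's own approach to the interaction.

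**What to change.** Add to the missed-dose paragraph of Section 5.2, as a recommendation of the same strength as the existing one: subjects on nintedanib who miss the planned IMP dose should not take it with, or shortly before, the evening nintedanib dose, and should skip it if they remember it only around that time.

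The words on taking it shortly before are needed because a bare instruction to keep the doses apart would allow IMP half an hour before nintedanib. The sponsor should define the interval from the CL-113 data, bearing in mind that the reported reduction is for IMP taken 2 or 4 hours after nintedanib. No number is proposed here because the visible documents do not support one.

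The cost is one sentence and a few more skipped IMP doses. Because treatment is blinded, the skips would fall in all three arms of the nintedanib stratum. Their number cannot be given. They would slightly lower the tablet-count compliance in SAP Section 9.2.6. They would not change which data enter the primary analysis, since SAP Section 4 uses data regardless of IMP interruptions.

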5.3. Packaging, Labeling, and Distribution

The film-coated tablet for oral use will be packaged in blisters.

All manufacturing, packaging, and labeling operations will be performed according to Good Manufacturing Practices (GMP) for Medicinal Products and the relevant regulatory requirements.

Each medication kit will be identified with a unique kit number. A multiple of kits will be provided to the subject at each visit, providing the subject with sufficient tablets to cover the period until the next scheduled visit.

The distribution to the clinical study center will only occur after all required documentation is obtained including clinical study approval by Competent Authorities and the IECs/IRBs, documentation on which the assessment of the investigator's qualifications was based (e.g. curriculum vitae), and the signed and dated study agreement and financial agreement. The IMP is to be dispensed according to the protocol.

In case study subjects cannot attend site visits, due to any COVID-19-related reason, direct-to-patient (DTP) shipment of IMP has been implemented and can be used to ensure the dosing regimen per protocol requirement can be maintained. DTP should only be used in case of emergency where on-site IMP dispensing is not possible, and if allowed per local regulations. Local guidelines must be followed and regulatory approval or notification of authorities may be required. The DTP process used will be reviewed and approved by the sponsor. If the DTP shipments originate from the investigational site(s), their coordination will be ensured by the

investigational site(s) in collaboration with the CRO to ensure clinical integrity without the involvement of the sponsor. Detailed guidance on the shipment has been provided to the sites in COVID-19 guidance documents. Consent of the subjects to receive IMP at home is required prior to the shipment of IMP, and should be documented in the source data. Return shipment of unused IMP from the subjects to the site may be implemented if allowed per local regulations.

5.4. Storage

Clinical study centers are to store all drug supplies in a secure, locked area with limited access below 30°C, protected from light, until dispensed. Clinical study centers will be required to monitor the storage temperature by using at least a calibrated minimum-maximum temperature-recording device and to keep a minimum to maximum temperature log, which must be completed each working day in order to establish a record of compliance with these storage conditions. The investigator will instruct subjects on how the IMP should be stored at home.

5.5. Treatment Compliance and Drug Accountability

For each dose taken at home, the date and number of tablets taken should be recorded on the subject diary card (see Section 6.4 for additional information). A new diary card will be provided together with each new medication kit. Any interruption or change in treatment (together with the reason for change) should be documented on the subject diary card.

The investigator or designated clinical study personnel will maintain a log of the total amount of IMP received at the clinical study center, amount dispensed to the subject, and the amount of IMP returned by the subject to the clinical study center. IMP supplies for each subject will be inventoried and accounted for throughout the clinical study. These records will be checked against the inventory by the study monitor on a regular basis. All clinical supplies will be stored in locked facilities.

Subjects will return any unused IMP and empty IMP packages at each study visit. Missed doses should be discussed to try to ascertain the reason(s). Every effort should be made to ensure proper subject dosing. Subjects with poor compliance will be re-trained by the clinical study center.

Treatment compliance will be assessed by the investigator or designee. At each visit, clinical study center staff will review treatment compliance by assessing the number of returned IMP.

